9.2.2.1 Sampling Strategy

On Day 1 of Course 1, serial blood samples for PD-0332991 (IBRANCE) pharmacokinetic studies will be collected at the following times: pre-dose and at 0.5, 1, 2, 4, 8 (± 1), 10 (± 0.5) [optional], 24 (± 4), and 48 (± 4) hours after the oral dose. **In order to obtain the 24 and 48-hour time points, the dose on Day 2 will be held. It is crucial that the 48-hour time point be obtained prior to dose administration on Day 3.**

On Day 21 of Course 1, serial blood samples for PD-0332991 (IBRANCE) pharmacokinetic studies will be collected at the following times: pre-dose and at 1, 2, 4, 8 (± 1), 10 (± 0.5) [optional], and 24 (± 4) hours after the dose (prior to the next administered dose).

For children less than 13 kg, contact [name] or his designee [REDACTED] for a sampling strategy with reduced blood requirements.

Pharmacokinetic Studies after Discontinuation of Dexamethasone (if consented)

Any patient who received dexamethasone during the mandatory PD-0332991 (IBRANCE) pharmacokinetic studies should have serial blood samples obtained at least 14 days after discontinuation of dexamethasone, and after 14 days of continuous dosing with PD-0332991 (IBRANCE). At a routine clinic visit samples for pharmacokinetic studies should be obtained at the following times: pre-dose and at hours 1, 2, 4, 8 (± 1), 10 (± 0.5) [optional], and 24 (± 4) hours after the dose (prior to the next administered dose).

9.2.2.2 Sampling Collection and Processing instructions

At each time point, 2 mL of blood will be collected into appropriately labeled tubes containing K₂EDTA. Two mL of blood is needed to provide approximately 1 mL plasma for pharmacokinetic analysis. Record the exact time that the sample is drawn along with the exact time that the drug is administered on the Pharmacokinetic Data Collection Form that is available on the PBTC-042 webpage.

During the sample collection and processing steps, the blood and plasma should be kept out of direct sunlight and unfiltered lab light. Upon collection of the blood PK samples in K₂EDTA blood collection tubes, keep the blood samples on wet ice at all times prior to processing to plasma. Samples will be centrifuged at approximately 1700 x g for about 10 minutes at 4°C (Note: If a refrigerated centrifuge is not available, please refer to the Shipping Manual located on the PBTC-042 webpage for further instructions). The plasma will be stored in an appropriately labeled amber screw-capped polypropylene tube at approximately -20°C within 1-hour of collection.

9.2.2.3 Handling of Specimens(s)

The blood to plasma sample processing requires using refrigerated centrifuges. The samples should be stored at -20°C. The established long-term stability (LTS) of PD-0332991 (IBRANCE) in frozen plasma stored at -20 °C or -70 °C is 439 days. Additional testing is to be conducted to extend the LTS.

9.2.2.4 Shipping of Specimen(s)

At the start of the study, each participating institution will receive a Pharmacokinetics (PK) kit from [name] for the collection of samples.

Samples should be shipped for delivery Monday through Thursday with a generous amount of dry ice enclosed to safeguard against shipping delays. Weekend and holiday deliveries should be avoided. Sites should contact the [name] Laboratory at St. Jude Children's Research Hospital, at [REDACTED] to request a Pharmacokinetics Kit for each patient enrolled on the study.

Samples should be shipped within 30 days of the last sample being taken. The site should use the PBTC-042 PK/PG FedEx account details, located on the PBTC member website. Ship all pharmacokinetic samples on dry ice along with a completed Pharmacokinetics Sample Transmittal Form (located on the PBTC 042 webpage in the "Protocol Specific Instructions/forms" section) to:

[name] Laboratory

[REDACTED]

Samples must be shipped from the site to the respective laboratory within 30 days of last sample collection in order to receive cost reimbursement. The sample collection and shipping dates must be documented in the eCRF.

9.2.2.5 Description of PD-0332991 Assay

PD-0332991 PK is measured in K2EDTA plasma samples. The LC-MS/MS-based method identifies both PD-0332991 and its lactam metabolite ((PF-05089326) but will be used for measuring PD-0332991 levels only. The assay is fully validated and meets the criteria for the validation method defined in the FDA and EMA Guidance documents and executed in a Pfizer approved US-based laboratory (not CLIA certified).

The method has been successfully used for the analysis of PD-0332991 PK samples from multiple Pfizer sponsored studies. The assay dynamic range for PD-0332991 is from 1 to 250ng/mL.

NOTE: The validated dilution may change depending upon the concentrations of the study samples outside the curve and are validated during the sample analysis phase if required more than a 10-fold dilution.

9.2.2.6 Description of Pharmacokinetic analysis

The PD-0332991 plasma concentration-time data will be analyzed with both compartmental and non-compartmental approaches. The noncompartmental analysis will provide an estimate of the maximum concentration (C_{max}), minimum concentration (C_{min}), area under the concentration-time curve, and apparent oral clearance.

Pharmacokinetic data will also be analyzed using nonlinear mixed effects modeling (NONMEM v.7). For PD-0332991, an appropriate compartmental pharmacokinetic model will be fit to the data. Estimated pharmacokinetic parameters may include the absorption rate constant (k_a), apparent oral clearance (CL/F), apparent volume of distribution (V_1/F), peripheral volume of distribution (V_2/F), and distributional clearance (Q/F). The typical population value and inter-individual variability of each parameter will be determined using NONMEM. Demographic and clinical chemistry covariates will be examined graphically (via individual Bayesian parameter estimates) and by using generalized additive modeling. Potentially significant covariates will be tested in the NONMEM population model.

9.3 Pathology and Exploratory Correlative Studies

The Pathology Central Review and Biorepository (CRB)'s function is to collect, distribute and store specimens for central pathology review and planned correlative studies which support the laboratory objectives of this protocol.

The CRB will also serve as a central repository for specimens collected for future research and left over specimens (tumor tissue, blood, urine or CSF) returned to the repository following the planned analysis from patients who consent to long term storage of unused specimen. These samples will be stored in the repository for undefined future studies which support the mission of the PBTC. **If the patient does not consent to participation in the repository, correlative study samples should be submitted following the guidelines in the appropriate correlative study section below (9.3.3). If the patient does not consent to long term storage, remaining correlative study samples will be destroyed once the PBTC-042 analysis is complete.**

9.3.1 PBTC CRB Submission Guidelines

If the patient consents to provide slides for submission to the repository at the time of participation in a PBTC trial, the following should be submitted:

- Tumor material
Slides from the original and/or recurrent surgery should be prepared for storage. The site should provide up to twenty (20) unstained sections cut at 4µm in thickness on (+) slides from the most representative section. For patients who have consented to other correlative studies (e.g. genomics) on this protocol that require slides, these submitted slides will be used for the conduct of studies outlined in the corresponding section below (9.3.3). Fewer unstained sections may be submitted based on size and availability of tissue. Preference is for tissue that has not previously been frozen. The corresponding pathology report (s) including immunohistochemical, special stains, and molecular/genetic results is to be uploaded to the PBTC using the secure File Upload system. These reports will be made available to the pathologist via a link in the ProtoLab.

- Suitability of sections would be established by preparing one (1) H&E to ensure that the sections meet the following criteria:
 - histologically representative of the reported lesion
 - contain at least 60% viable tumor
 - no more than 40% necrosis

- Peripheral Blood Mononuclear Cells and Plasma
PBMC may be collected by processing a 2-5 mL whole blood specimen with Ficoll or collecting the specimen in a BD Vacutainer™ CPT™ Cell Preparation Tube with Sodium Citrates as noted below. Once separated, all pellets must be snap frozen and stored at least at -20°C prior to dry ice shipment.

Specimen Collection and Processing by Ficoll tube

- Collect 2 – 5 mL of fresh blood into an EDTA tube.
- Transfer blood into a sterile 50-mL tube and add double the amount of PBS. MIX GENTLY.

- Set up another tube containing half of its total volume of Ficoll. For example, if there is 15 mL of blood + PBS, then use 7.5 mL of Ficoll (2:1 ratio).
- At very slow pace (approx. 2 mL/minute), layer the blood + PBS mixture onto the Ficoll so that the solutions DO NOT MIX. Spin the blood/Ficoll at 750 g in slow mode for 30 minutes @ 25°C. After spin you will see four distinct layers: plasma (top layer), white fluffy ring (2nd layer), Ficoll (3rd layer), and blood (bottom layer).
- Remove plasma layer down to about 1 mL above the white fluffy ring and dispense into cryovials. Freeze the cryovials within 1 hour of collection and store immediately at -20°C or colder.
- Collect the entire white fluffy ring. If ring is hard to see, also take extra liquid above. Then discard everything else.
- Place this fraction of white blood cells into a fresh 50 mL sterile tube with 20 mL of PBS. Spin down for 10 minutes @ 25°C, 750 g in fast mode. Remove the supernatant. Add back to pellet 1 mL of PBS and spin for 5 min. at 4°C at 10000rpm. Remove supernatant.
- Freeze the pellet of WBCs and store at -80°C until shipment.
- Ensure that all tubes are clearly labeled with the PBTC patient accession number. Please ensure that the labeling system used is designed to withstand temperatures down to -80°C. Samples should be stored at -80°C until shipment. For short term storage (2-3 weeks) -20°C is acceptable. NOTE: 4°C IS NOT ACCEPTABLE STORAGE.

If it is not possible to collect the PBMC by Ficoll gradient then separation of PBMC can be conducted using CPT tube separation as an alternative. However the PBMC pellet MUST BE frozen immediately and stored at -80°C.

Collection and Processing by CPT tube

- Peripheral blood should be collected in a BD Vacutainer CPT™ Cell Preparation Tube with Sodium Citrate. 8 mL and 4 mL CPT tubes can be obtained from Fisher Scientific (Cat# 02-685-125, 02-688-81) or Becton-Dickinson (BD No.362761, 362760). The 8 mL tubes have a 6 mL minimum draw and the 4 mL tubes have a 3 mL minimum draw.
- Centrifuge the CPT™ tube at 1500 x g for 30 minutes at room temperature (20° C to 25° C). DO NOT APPLY THE BREAK ON THE CENTRIFUGE. Use acceleration 5, brake 0 (“slow mode”).
- It may be necessary to spin the tube longer to ensure that all of the red blood cell components have been separated from the plasma layer through the polyester gel barrier.
- The tube should be removed immediately from the centrifuge. The mononuclear layer and plasma lie above the polyester gel plug.
- Using a sterile stripette, remove as much of the plasma component (upper half of the CPT tube) without disturbing the mononuclear layer if possible and aliquot it into cryovials. Freeze the cryovials within 1 hour of collection and store immediately at -20°C or colder.
- Transfer mononuclear cell layer (and some residual plasma layer) to a labeled 15-mL conical centrifuge tube and add 5 mL sterile room temperature magnesium or calcium-free phosphate buffered saline (PBS) to fill the conical tube and recap.
- Centrifuge at 450 x g for 10 minutes at room temperature (20° C to 25° C). Use acceleration 9, brake (“fast mode”).
- Remove supernatant, being careful not to aspirate the cellular pellet at the bottom of the tube.

- Add 1mL of sterile PBS to the pellet and gently re-suspend by pipetting up and down. Transfer the entire suspended pellet to the labeled cryovial.
- Centrifuge the cryovial at 450 x g for 5 minutes (or spin down the microcentrifuge tube at 1300 x g for 5 minutes) at room temperature. Discard the supernatant.

Store the cell pellet cryovial frozen at -80°C. For short term storage (2-3 weeks) -20° C is acceptable.

If the patient consents to other secondary correlative studies as outlined in section [9.3.3](#), the following specimens may also be submitted to the CRB for distribution and storage.

- Formalin-fixed, paraffin-embedded (FFPE) slides or an FFPE tissue: quantity and schedule of collection as outlined in section [9.3.3](#).

9.3.1.1 Handling of Specimens

- Slides are to be labeled with the study ID and the patient PBTC Accession # and these slides should be designated as PBTCR # (where the # assigned from 1 to 20, or the highest number of unstained sections prepared, sequentially) or PBTCR H&E for the H&E stained section.
- Formalin Fixed, Paraffin Embedded (FFPE) tumor materials are to be labeled with the PBTC Accession # and the PBTC study for which the sample is provided. FFPE tumor material should be shipped at room temperature.
- PBMCs are to be labeled with the PBTC Accession # and the PBTC study for which the sample is provided. Samples should be shipped overnight in a separate box with a 2-day supply of dry ice unless otherwise specified.

9.3.1.2 Shipment of Specimens

Samples collected for the repository should be sent to the PBTC CRB overnight via FedEx Monday through Thursday by completing the Internet form at <http://www.fedex.com/us/> and requesting FedEx to e-mail [contact]. FedEx user ID and password for pathology shipping can be found at PBTC-042 protocol webpage. Samples should be shipped in the appropriate environment as described in Section [9.3.1.1](#). Samples are to be shipped to:

PBTC CRB

[REDACTED]

9.3.2 Pathology Central Review

Central pathology review is optional for this study. In consenting patients, samples for central pathology review will be completed from the slides submitted to the PBTC CRB.

Pathologist review for this study will include the following elements:

- Examination of H&E stained slides and, if the tumor being reviewed is residual, recurrent or metastatic, examination of H&E slides from the original primary tumor. For each subject one (1) H&E stained slide per one representative block from the brain tumor, removed either at initial diagnosis or relapse, should be submitted for review.
- Review of the corresponding pathology report(s) of the immunohistochemical, special stains, and molecular/genetic results from current and/or original primary tumor
- If necessary, review of immunohistochemical or special stained slides. Slides submitted to the PBTC CRB will be digitized to 40X. H&E stained sections will be retained and filed at the CRB. Original immunohistochemical or special stain slides will be returned to the submitting institution.

9.3.3 Assessment of Cyclin D1, Cyclin D2, Cyclin D3, CDK4, CDK6, and Ink4a-ARF loss

Description of Assay

Array CGH is a superior approach to detect amplifications and deletions of genes such as cyclin D1, cyclin D2, cyclin D3, CDK4, CDK6, and Ink4a-ARF loss. The assay will be array CGH using the Agilent 1M microarray. Minimum required genomic DNA from FFPE tissue is 2,000 ng. Ten unstained FFPE slides would be required (although it depends on the genomic DNA yield per slide). It is of particular interest to look for the following copy number variations: Cyclin D1, Cyclin D2, Cyclin D3, CDK4, CDK6, Ink4a-ARF loss, and possibly others. The median probe spacing is 2.1-kb which allows for the detection of smaller more focal amplifications and deletions.

9.3.3.1 Collection of Specimen(s)

10 unstained slides from formalin fixed, paraffin wax embedded (FFPE) tumor material will be collected at the time of enrollment from all patients who have agreed to participate in this correlative study.

Either 10 unstained 5 um formalin-fixed, paraffin-embedded (FFPE) slides or an FFPE tissue block from tumor material will be collected. Use air-dried non-charged, non-coated slides. Oven drying of slides should be avoided. Samples must be labeled with the PBTC accession number, protocol number and date of collection. Specimens should be shipped at room temperature along with a completed Specimen Transmittal Form found on the PBTC-042 website.

9.3.3.2 Handling of Specimens(s)

FFPE slides or tissue blocks should be stored at room temperature.

9.3.3.3 Shipping of Specimen(s)

The slides should be shipped at room temperature to the PBTC CRB Monday through Thursday via Federal Express Priority Overnight using the FedEx account information and transmittal form, found on the PBTC-042 Protocol and Resources web page. Weekend deliveries are not permitted. Receipt and processing of biological materials will be recorded in ProtoLab, as appropriate, by staff at the PBTC CRB. The sites sending the materials must document sample

collection and shipping dates in the eCRF. Specimens should be sent to the following address:

PBTC CRB

[REDACTED]

9.4 Neuroimaging Studies

Patients will have MRI brain with and without contrast performed prior to initiation of therapy, after courses 2, 4, 6, then every 12 weeks and at the time of end of treatment. MRI Spine should be performed prior to therapy and at the same time points as standard MRI brain, if clinically indicated.

9.4.1 Image Transfer

Only scans showing a response, the confirmation scan obtained approximately 8 weeks later if available and the corresponding baseline scan will be electronically transferred to the PBTC Neuroimaging Center (NIC) for central review.

All patient specific data are stripped from the images and replaced with PBTC Subject Accession number prior to transmitting the images to the NIC. All image data transfer is accomplished using pretty-good-privacy (PGP) 128-bit encryption, which meets industry standard for secure communication.

9.4.2 Discipline Review: Neuro-imaging

Local review of MR imaging studies at each site and central review of the MR imaging studies will be conducted through the PBTC Neuroimaging Center (NIC). The director and one Neuroradiologist of NIC will review the imaging studies at study completion. If the local and central review are not in agreement the NIC neuroradiologist will confer with the participating site to determine why there is a discrepancy via conference call.

NIC review will include assessment of response to therapy (as feasible). All patients with a documented PR/CR at any time point will have central review of the scan showing response, the confirmation scan obtained approximately 8 weeks later, as well as the corresponding baseline scan conducted for confirmation.

10 STUDY CALENDAR

	Pre-therapy	Course 1	Course 2- Course 26	Completion/ Discontinuation Of Treatment
PHYSICAL ASSESSMENTS				
Medical history	X	Weekly	X	X
Physical exam /height/weight	X	Weekly	X	X
Vital signs	X	Weekly	X	X
Performance status	X	Weekly	X	X
Neurologic exam	X	Weekly	X	X
LABORATORY EVALUATIONS				
CBC - WBC, HgB, Hct, Platelets, ANC, ALC	X	Weekly ^A	Weekly ^{A, B}	X
Serum Chemistry - Sodium, Potassium, Bicarbonate, Chloride, Calcium, BUN, Creatinine, Glucose, Phosphorous, Magnesium, Albumin, Total Protein	X	Weekly	X ^B	X
SGPT (ALT), SGOT (AST), Alkaline phosphatase, Total Bilirubin	X	Weekly	X ^B	X
Serum pregnancy test (for females of childbearing potential)	X	X ^B	X ^B	
CSF cytology (if clinically indicated)	X			
OTHER ASSESSMENT				
12-lead EKG	X	X ^C	X ^C	X ^C
Ophthalmology Examination (including slit lamp)	X		X ^D	
IMAGING ASSESSMENTS				
Brain MRI (standard)	X		X ^E	X
Spine MRI (if clinically indicated)	X		X ^F	X
CORRELATIVE STUDIES				
Screening Pre-trial tumor materials for Rb1 testing (required for patients with all types of CNS tumors except DIPG, medulloblastoma, ATRT)	X ^G			
Pharmacogenetic Studies (if consented)	X ^H			
Plasma Pharmacokinetic Studies (required)	X ^I	X ^I		
Plasma PK after discontinuation of dexamethasone (if consented)		Any time after stopping dexamethasone ^I		
Pre-trial tumor materials for Genomics (if consented)	X ^J			
Tumor Tissue and blood for Biorepository (if consented)	X ^K			

	Pre-therapy	Course 1	Course 2- Course 26	Completion/ Discontinuation Of Treatment

A. CBC with differential at baseline and q weekly during each cycle for the first 3 cycles; consideration can be given to increase interval to q 2 weeks from course 4 onwards if the patient has no DLT in the previous cycle. If patient develops Grade 4 neutropenia or thrombocytopenia, then CBCs should be checked every 3-4 days until recovery to Grade 3.
 
B. Within 48 hours of beginning protocol therapy and each course (see 5.3).
 
C. 12-lead EKG at baseline, and 3 hours post dose on days 1, 8, and 15 of cycle 1 and on day 1 of cycles 2 and 3. Thereafter, EKG should be done prior to the start of every 3rd cycle (prior to 6, 9, 12, 15, 18, 21, 24 and end of treatment).
 
D. Eye exam is to be done at baseline, and every 3 months (after courses 3, 6, 9, 12, 15, 18, 21, 24). The ophthalmology exam report should clearly specify the presence or absence of cataracts and data must be recorded in Rave database.
 
E. Standard imaging is to be done every 8 weeks (after courses 2, 4, 6) and then every 12 weeks thereafter through the 26 courses and at the completion of treatment.
 
F. MRI Spine should be done at the same time points as the standard MRI brain, if clinically indicated.
 
G. 2 unstained slides from FFPE block and 1 H&E slide required to be submitted for Rb testing (see 9.1.1)
 
H. Obtain 5 mL of whole blood prior to 1st dose if consented (See section 9.2.1 for details)
 
I. Plasma PK (required) – D1 Course 1: pre-dose, 0.5, 1, 2, 4, 8, 10, 24, 48 hrs after dose D21 Course 1: pre-dose, 1, 2, 4, 8, 10, 24 after dose (See section 9.2.2 for details of Plasma PK) Plasma PK after discontinuation of dexamethasone (if consented) – see section 9.2.2
 
J. 10 unstained slides from FFPE block or FFPE tissue block [See section 9.3.3 for details of Pre-trial tumor materials for Genomics (if consented)]
 
K. Biorepository samples (if consented) – 20 unstained FFPE slides and blood. Obtain 2-5 mL of whole blood at baseline. If unable to collect at baseline, it can be collected any time during protocol therapy. See section 9.3.1 for details.
				

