2.4.2 Rationale for Pharmacokinetic Studies

Because the pharmacokinetics of this agent are relatively unknown in the pediatric population, this information will be essential for evaluating toxicity and disease response and for refining dosing in future clinical trials of PD-0332991. The results of these studies will provide the basis for assessing the relationship between the disposition of PD-0332991 in adult and children. Mandatory pharmacokinetic studies are needed to characterize the disposition of PD-0332991 in this patient population. Insights into the biologically active dosage will be gained by relating PD-0332991 systemic exposure (e.g., AUC) to results of pharmacodynamic studies (e.g., percentage change in ANC and platelets compared to baseline).

In vitro studies indicate that PD-0332991 is a substrate of CYP3A4, and dexamethasone is a known inducer of CYP3A4. Thus, one might expect lower exposures of PD-0332991 when administered concurrently with dexamethasone. Indeed, following multiples doses of PD-0332991 in A5481004 Phase 2 (dosing Schedule B), the mean PD-0332991 24-hr trough drug concentrations seem to decrease with time. The mean PD-0332991 trough concentrations on Cycle 1 Day 8, Cycle 1 Day 11, and Cycle 2 Day 11 were 45.33, 44.09, and 32.00 ng/mL, respectively, which is suggestive of a decreased PD-0332991 exposure when administered after dexamethasone-mediated enzyme induction has occurred. It should be noted that the exposure of PD-0332991 observed in this study is considerably lower compared to those observed in Studies A5481001 and A5481003 at the dose levels likely due to the induction effect of dexamethasone. Hence, patients who are receiving dexamethasone will have optional plasma PK studies done following discontinuation of this drug.

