5.1 Agent Administration

PD-0332991 (IBRANCE) is currently available as 75, 100, and 125 mg capsules (No liquid formulation is currently available). PD-0332991 (IBRANCE) will be given oral daily for 21 days followed by a week rest (one course = 28 days) for 24 months (26 courses). The starting dose will be 50 mg/m²/day for stratum I. The starting dose for stratum II will be one dose level below the MTD for stratum I (50 mg/m²/day).

Dosing is based on BSA calculated at the beginning of each course of therapy. The dose prescribed should be rounded to the nearest deliverable dose based on the BSA adjustment and the available capsule sizes. Dosing Tables are available in [Appendix D](#). Patients will be provided with a Medication Diary for PD-0332991 (IBRANCE), instructed in its use, and asked to bring the diary as well as the remaining capsule bottles with them to each appointment. The Patient Diary is available on the PBTC-042 webpage.

PD-0332991 (IBRANCE) should be taken with food. Patients are encouraged to take their dose at approximately the same time each day. Capsules should be swallowed whole (do not chew, crush or open them prior to swallowing). Capsules should not be ingested if they are broken, cracked, or otherwise not intact. Patients should be advised to drink plenty of water or take hydration fluids to avoid dehydration if diarrhea occurs. Patients who vomit a dose of PD-0332991 (IBRANCE) can be re-dosed if capsule is intact in the vomitus, and appropriate anti-emetic therapy should be implemented prior to the next scheduled dose (see [Appendix B](#) for contraindicated anti-emetic medications).

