5.4 Concomitant Medications and Supportive Care Guidelines

5.4.1 Steroids

Corticosteroids should be used at the lowest dose to control symptoms of edema and mass effect, and discontinued, if possible. Use of corticosteroids should be recorded in the Rave database.

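### After course 1 no EKG is timed near steady state, except possibly the end-of-treatment one; a patient who stops dexamethasone could have QTc read on drug at the visit already planned for repeat PK (cheap improvement, low severity)

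*Combined protocol and SAP*

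**What the plan says.** Footnote C of section 10 places on-treatment EKGs "3 hours post dose on days 1, 8, and 15 of cycle 1 and on day 1 of cycles 2 and 3". It continues: "Thereafter, EKG should be done prior to the start of every 3rd cycle", listing cycles 6, 9, 12, 15, 18, 21 and 24, and adds one at end of treatment. No window is given for the pre-cycle EKGs and no dose timing for the last one. No other section schedules an on-treatment EKG.

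Section 5.1 gives drug daily for 21 days, then a week of rest, for up to 26 courses. It adds: "Dosing is based on BSA calculated at the beginning of each course of therapy".

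On steroids, section 5.4.1 says: "Corticosteroids should be used at the lowest dose to control symptoms of edema and mass effect, and discontinued, if possible". Section 2.4.2 treats dexamethasone as a CYP3A4 inducer and cites an adult study in which mean troughs were 45.33 ng/mL (cycle 1 day 8), 44.09 (cycle 1 day 11) and 32.00 (cycle 2 day 11), "which is suggestive of a decreased PD-0332991 exposure when administered after dexamethasone-mediated enzyme induction has occurred". For patients who were on dexamethasone during the course 1 PK, section 9.2.2.1 offers, by consent, a second serial profile. It comes at least 14 days after dexamethasone stops and after 14 days of continuous dosing, with samples pre-dose and at 1, 2, 4, 8 and 24 h (10 h optional).

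**The concern.** Section 2.2.2.1 reports hERG, Purkinje-fiber and dog findings that point to a QT risk, and the protocol schedules EKGs for as long as two years. An EKG shows an acute, concentration-driven QTc effect only if drug is on board. After course 1, the two dose-timed EKGs follow the first dose after a drug holiday, and the seven periodic ones come before dosing resumes.

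For a patient with constant exposure this costs little, because course 1 has already answered the question. It matters when the patient's own exposure rises later. The clearest route is one the protocol itself anticipates: dexamethasone on board in course 1, then withdrawn. That patient's steady-state EKGs may have been read at induced, lower exposure, and no scheduled EKG is timed to the higher steady state. A secondary route is a BSA recalculation that crosses a capsule step. What is at stake is the safety of the individual patient.

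**Working it through.** **Count.** Every third cycle from 6 up to 26 gives 6, 9, 12, 15, 18, 21, 24, which is seven and matches footnote C. After course 1 there are 2 + 7 EKGs plus end of treatment.

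**Inputs (adult values; pediatric PK is assumed similar).**
- Half-life: 26.5 h (section 2.2.3.3, Table 5) and about 22.6 h (Table 6).
- Tmax: 4.2 h (Table 5) and 4-12 h (Table 6, large-particle freebase capsule, fasted volunteers; trial patients dose with food).
- Dosing: days 1-21, with the course 1 day 2 dose held (section 9.2.2.1).

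**Model.** One compartment with first-order absorption. k = ln2/t½, and ka is solved from Tmax = ln(ka/k)/(ka − k). Concentration is the sum over doses of ka/(ka − k) × [exp(−kτ) − exp(−kaτ)], where τ is the time since each dose. The reference is the same patient's level 3 h after the course 1 day 15 dose.

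**Hand check at 26.5 h.** k = 0.693/26.5 = 0.0262 per h. Accumulation = 1/(1 − exp(−24k)) = 2.14, against a stated median of 2.4 (range 1.5-4.2). A first dose after the rest week is then about 1/2.14 = 47% of steady state; the full model gives 45% at Tmax 4.2 h. From the day 21 dose to the next cycle start is 192 h, or 192/26.5 = 7.2 half-lives, leaving exp(−192k) = 0.7%.

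**Results, relative to the course 1 day 15 level.**

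| EKG time | t½ 22.6-26.5 h, Tmax 4-12 h | t½ 40 h |
|---|---|---|
| Course 1 day 8, 3 h | 98-99% | 93-94% |
| Cycle 2 or 3 day 1, 3 h | 27-50% | 24-37% |
| Pre-cycle, day 22 (24 h after last dose) | 55-80% | 71-85% |
| Pre-cycle, day 23 (48 h) | 26-43% | 47-56% |
| Pre-cycle, last 48 h (144-192 h) | 0.3-3.5% | 3.9-10.6% |

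At the extreme stated accumulation of 4.2 (effective half-life about 61 h), a first dose is 1/4.2 = 24% of steady state, and 11% of the day 21 level remains at 192 h.

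**How large a later rise might be (upper-end values).**
- Dexamethasone: 45.33/32.00 = 1.42, or +42%. This inverts a trough difference from one adult study that the protocol calls only suggestive. Section 2.4.2 does not give that study's dexamethasone dose.
- Capsule step, dose level 1 (Appendix D): (100/1.76)/(75/1.75) = 56.8/42.9 = 1.33. Dose level 2: (100/1.17)/(75/1.16) = 85.5/64.7 = 1.32. Both need a starting BSA at the very top of its band. From BSA 1.50 at level 1 the change is 56.8/50 = 1.14.

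**Effect of such a rise (× 1.33 to 1.42).** Cycle 2 or 3 day 1 EKGs would be at 35-71% of the course 1 day 15 level, and late-rest-week EKGs at 0.4-5.0%. An EKG 3 h post dose on day 15 would be at 133-142%. For the scheduled EKGs to reach the level already checked in course 1, exposure would have to rise 1/0.503 = 2.0 to 1/0.266 = 3.8 fold (cycle 2 or 3 day 1), or at least 1/0.035 = 28 fold (last 48 h before a cycle).

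**The case against.** The main safety question is answered in course 1. The day 8 and day 15 EKGs are 3 h post dose at 98% or more of steady state with the stated half-lives. A reader might infer that steady-state QTc is never checked; footnote C shows otherwise.

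A reader might also infer that patients reach unmonitored doses. They do not. At level 1 the stepped-up 56.8 mg/m² is below the 62.5 mg/m² (75/1.20) of a patient at the minimum BSA. At level 2, 85.5 mg/m² is what a patient entering at BSA 1.17 receives in course 1. Stopping dexamethasone likewise returns a patient to the un-induced exposure at which patients not on dexamethasone have course 1 EKGs. The cohort description of toxicity therefore loses little.

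The margin is reassuring. Dogs showed no ECG effect at unbound Cmax of 42-80 ng/mL, against 18 ng/mL in humans at 125 mg (2.3 to 4.4 fold). That 18 looks un-induced (18/104 = 17%, within the stated 12-19% unbound), so stopping dexamethasone moves a patient toward it. Even the level 2 step, scaled from the 75 mg/m² adult equivalent, gives 18 × 85.5/75 = 20.5 ng/mL. Adult trials had no Grade 3 QTc prolongation on the 14-day schedule and one mild event, judged unrelated, on the 21-day schedule. The CAEPR does not list QT prolongation. Entry excludes QTc above 450 msec.

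All of this stands and sets the severity. Three qualifications remain. Drug exclusions do not close every route: section 5.4.9 disallows the Appendix C drugs, but Appendix C only advises against moderate CYP3A inhibitors. The pre-cycle EKGs are not necessarily drug-free, because an EKG at day 22 would be informative; but nothing directs sites there, and footnote B ties other course-start tests to the last 48 h. Unscheduled EKGs are not forbidden, but none is prompted.

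Moving every later EKG to day 15 is also tempting. Examinations after course 1 are per course, and section 3.4 lets laboratory tests be done elsewhere, so this could mean seven to nine extra dose-timed visits for some families. The low risk does not justify requiring that.

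**Conclusion.** The timing gap is real and small. After course 1 no EKG is scheduled near steady state, except possibly the untimed end-of-treatment one. Those on day 1 of cycles 2 and 3 would catch part of a rise already present by then. From cycle 4 on, an on-drug effect would be seen only if a pre-cycle EKG happened to fall early in the rest week, at end of treatment, or on an unscheduled tracing.

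The gap is one of individual safety, chiefly for a patient on dexamethasone in course 1 who later stops; the BSA step is secondary. The documents do not show that QTc prolongation is likely, and dose escalation is not touched. Few patients are involved: stratum I is closed, and stratum II is capped at 18, with 4 enrolled as of version 8.0.

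The percentages rest on a one-compartment model, adult PK and partly fasted Tmax values. The ordering of the time points holds across every half-life tried. The +33% and +42% are upper-end figures, not expected values.

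**What to change.** Amend footnote C in two places.

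1. For any patient who has the post-dexamethasone PK visit of section 9.2.2.1, take the next due EKG about 3 h post dose at that visit. The patient is already there between the 2 h and 4 h samples, at steady state, so this adds no visit and no EKG.
2. Record time since last dose for every EKG, including the one at end of treatment.

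Optionally, where a patient already attends the primary site on about days 15-22, take the periodic EKG then instead of at the end of the rest week. Footnote A's "consideration can be given to increase interval to q 2 weeks from course 4 onwards" is compatible with a day 15 blood count. Do not require moving all later EKGs to day 15.

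Cost: a footnote amendment, one data field, and one fewer pre-cycle (or cycle 2 or 3 day 1) EKG for the affected patients. Section 5.3 does not use QTc as a criterion for starting a course, so no decision rule is lost. The repeat PK visit is by consent, so some patients who stop dexamethasone will still not be covered.
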